15.8.2 Clinical study registration

Takeda Pharmaceutical Company Limited will ensure timely publication of the information of a clinical study and registration of all clinical researches in patients under way all over the world, prior to study initiation, with ClinicalTrials.gov, JAPIC, and UMIN to comply with the applicable laws/regulations and guidelines. The city and country where a study is performed, and the subject recruitment status should be registered as well as the contact information of Takeda Pharmaceutical Company Limited to enable general access.

15.8.3 Clinical trial results disclosure

Takeda Pharmaceutical Company Limited will post the results of a clinical study on ClinicalTrials.gov, JAPIC, and UMIN as specified by the applicable laws and/or regulations irrespective of results.

15.8.4 Method of storage and destruction of material/information concerning clinical study

The director of the study site should appropriately retain the material/information related to this study for at least to the date passing 5 years from the date of reporting of the ending of the study from the investigator or to the date passing 3 years from the date of reporting of final publication of the study result, whichever date is later.

CONFIDENTIAL

15.9 Insurance and compensation for injury

The subjects participating in this study will be compensated for any injury resulting from participation in the study according to local regulations applicable to the study site. It should be noted that any treatment provided will be covered by health insurance, and no monetary compensation will be provided.

Appendix A Evaluation according to RECIST ver 1.1

Evaluation will be conducted according to RECIST ver 1.1 as follows.

1. Definition of measurable lesion

Lesion that fulfills any of the conditions below will be considered as a measurable lesion.

- (1) Lesions other than malignant lymph node (non-nodal lesion) that meet either of the below
 - 1) CT scan slice thickness no greater than 5 mm or MRI largest diameter at least 10 mm
 - 2) CT scan slice thickness greater than 5 mm or MRI largest diameter is 2 folds or more the slice thickness
- (2) Malignant lymph node CT scan slice thickness 5 mm or less and short diameter at least 15 mm
(Malignant lymph node with short diameter at least 10 mm and less than 15 mm will be a non-target lesion, lymph node with short diameter of less than 10 mm will not be considered as a lesion)

Any other lesion besides the above will be considered as non-measurable lesions.

Note that lesions below will be considered as non-measurable lesions irrespective of test method or size of lesion:

- Bone lesions
- Cystic lesions
- Tumour lesions situated in a previously irradiated area, or in an area subjected to other loco-regional therapy
- Leptomeningeal disease lesion
- Ascites, pleural effusion, pericardial effusion
- Lymphangitic involvement of skin or lung
- Abdominal masses/abdominal organomegaly identified by physical exam that is not measurable by reproducible imaging techniques

2. Baseline documentation of target lesions

From measurable lesions observed before initiation of protocol treatment, select 5 lesions highest in diameter (long diameter for non-nodal lesion and short diameter for malignant lymph node), 2 lesions at most for 1 organ and determine them as target lesions. Upon selection, organs with measurable lesions should be included evenly, and select in consideration of those that lend themselves to reproducible repeated measurements (lesions with large diameter but difficult to measure should be avoided).

For chosen target lesion, in order from head to tail, record site, lesion diameters (long diameter for non-nodal target lesions, short axis for nodal target lesion) and a sum of diameters (hereinafter referred to as SoD) of all target lesions should be recorded.

3. Baseline documentation of non-target lesions

Lesions not selected for target lesion should be recorded as present or absent non-target lesion irrespective of whether measurement is possible or not. Multiple non-target lesions in the same

organ can be recorded as 1 lesion (e.g. multiple enlarged pelvic lymph nodes, multiple liver metastases)

4. Tumor response criteria

Evaluate target lesion and non-target lesion using the same method as at enrollment according to “9.2.10 Imaging test (thoracoabdominal-pelvic CT/MRI)“, and record diameter of target lesion, presence or absence of non-target lesion or onset of new lesion.

5. Response criteria of target lesion

• CR (Complete Response):

Disappearance of all non-nodal target lesions and all lymph node target lesions short axis <10mm If nodal target lesion is selected at baseline, response criteria may be CR even though SoD is not 0 mm.

• PR (Partial Response):

At least a 30% decrease in the SoD of target lesions, taking as reference the baseline SoD.

• PD (Progressive Disease):

Taking as reference the smallest sum on study (this includes the baseline sum if that is the smallest on study), at least a 20% increase in the SoD of target lesions, and the sum must also demonstrate an absolute increase of at least 5 mm.

• SD (Stable Disease):

Neither sufficient shrinkage to qualify for PR nor sufficient increase to qualify for PD, taking as reference the smallest SoD while on study.

• Not all Evaluated:

When test cannot be conducted for some reason, or cannot be determined as CR, PR, PD or SD.

$$\text{Reduction ratio of SoD} = \frac{\text{SoD before treatment} - \text{SoD at evaluation}}{\text{SoD before treatment}} \times 100\%$$

$$\text{Increase ratio of SoD} = \frac{\text{SoD at evaluation} - \text{Smallest SoD}}{\text{Smallest SoD}} \times 100\%$$

* Diameter of target lesion is recorded with actual measurements (e.g., even if under 5 mm) as much as possible, but when target lesion is determined as “too small to measure”, irrespective of CT slice thickness, if it is determined that tumor lesion no longer exists and the diameter will be recorded as 0 mm, whereas if it is determined to exist the diameter will be 5 mm.

- * If reduction ratio meets the PR criteria and increase ratio meets the PD criteria at the same time, criteria will be determined as PD.
- * If one lesion is divided during treatment, each diameter should be added to the SoD.
- * If multiple lesions agglutinate and the border cannot be distinguished, the diameter of the agglutinated lesion should be added to the SoD.
- * Whenever lesions are in contact, if the borders of the lesions are distinguishable, the diameter of each lesion should be added to the SoD.

6. Response criteria of non-target lesion

- CR (Complete Response):
Disappearance of all non-nodal non-target lesions and all lymph nodes short axis <10mm
- Non-CR/non-PD:
Persistence of one or more non-target lesion(s) including lymph nodes short axis \geq 10 mm and/or maintenance of tumor marker either of which the level is above the common normal limits.
- PD (Progressive Disease):
“Uequivocal progression” of existing non-target lesions (including recurrence).
When the patient has measurable lesion: In this setting, to achieve “unequivocal progression” on the basis of the non-target disease, there must be an overall level of substantial worsening in non-target disease such that, even in presence of SD or PR in target disease, the overall tumor burden has increased sufficiently to merit discontinuation of therapy. When response criteria for target lesion is SD or PR, an increase of non-target lesion that will overwhelm the tumor burden decrease will be determined as “unequivocal progression”, and if not it will be Non-CR/non-PD.
When the patient has only non-measurable lesion: a 20% increase diameter in a non-measurable lesion, an increase in tumor burden representing an additional 73% increase in ‘volume’ will be determined as “unequivocal progression”.
- Not all Evaluated:
When test cannot be conducted for some reason, or cannot be determined as CR, Non-CR/non-PD, or PD.

7. Appearance of new lesions

When a lesion that was not present at baseline has been observed after initiation of treatment, this will be determined as appearance of “new lesion”. However, “new lesion” should not be attributable to differences in scanning technique, change in imaging modality or findings thought to represent something other than tumor. For example, necrosis of a liver lesion may be

reported as a “new” cystic lesion, which it is not. A newly identified lesion in a location by test that was not mandatory at baseline (evaluation before enrollment) is considered a new lesion. If a lesion disappears and reappears later, measurement will be continued. However, the response at the time of reappearance of the lesion will be different depending on other lesions. If lesion has reappeared after CR, it will be determined as PD at the time of reappearance. On the other hand, if it was PR or SD, when the once disappeared lesion reappears, in order to calculate the response, the diameter of the lesion will be added to the rest of the lesions. Thus, when there are a number of lesions still existing, if one lesion apparently “disappears” and reappears later, from that alone, it will not be determined as PD but if the SoD of all the lesions meet the PD criteria, it will be determined as PD. The reason for this is that there is an understanding that most of the lesions do not truly “disappear” and yet it cannot be extracted due to the limit to resolution of imaging modality.

If there is a possibility of new lesion but cannot be confirmed, it should not be determined as a new lesion but re-examination by imaging test should be conducted after clinically appropriate interval. If new lesion is confirmed by imaging test re-examination, the date of the imaging test that confirmed the new lesion will be the time point for appearance of new lesion.

8. Overall Response

Overall Response will be determined with combination of target lesion response, non-target lesion response, appearance of new lesion according to Tables A.1 and A.2 below.

Table A.1 Overall response at each time point: When patient has target lesion (with or without non-target lesion)

Target lesion	Non-target lesion	New lesion	Overall response
CR	CR	Absent	CR
CR	Non-CR/non-PD	Absent	PR
CR	Not determined	Absent	PR
PR	Non-PD or defect in evaluation	Absent	PR
SD	Non-PD or defect in evaluation	Absent	SD
Defect in evaluation	Non-PD	Absent	NE
PD	Any	Present or absent	PD
Any	PD	Present or absent	PD
Any	Any	Yes	PD

9. Best Overall Response

Response will be more favorable in the following order: CR>PR>SD>PD>NE. The most favorable overall response through the entire course will be the best overall response.

When response could not be determined by imaging due to an obvious aggression of disease or death before the first response determination, it will be determined as PD. When response could not be determined by imaging due to discontinuation from toxicity or rejection by subject before the first response determination, it will be determined as NE.

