13.3.3 Efficacy analysis

13.3.3.1 Primary endpoint and analysis method

[Primary endpoint]

PFS rate 6 months after enrollment

The PFS rate 6 months after enrollment, the primary endpoint, is the gross proportion of surviving subjects without documented progression up to 6 months after enrollment, counting from the day of

CONFIDENTIAL

enrollment. Subjects with no imaging data on progression at 6 months after enrollment and subjects lost to follow-up will be included in the denominator, but will not be handled as progression-free.

The criteria for determining progression are described in “13.3.3.2 Secondary Endpoints and Analytical Methods for Them”.

[Main analysis]

The following analysis will be performed in the “full analysis set”.

PFS rate at 6 months is calculated by counting of subjects each subjects with progression, not progression, or unconfirmed at 6 months. “At 6 months” in the main analysis is defined as 24 weeks (8 weeks x 3) with time window of 2 weeks before and after. Based on the observed PFS rate at 6 months from the day of enrollment, binomial test will be conducted on the null hypothesis “value will be determined invalid at PFS rate $\leq 29\%$ ”. Significant level will be 2.5% (one-sided) in main analysis. For interval estimation, accurate 90% confidence interval (two-sided) based on binomial distribution will be used.

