13.3.3.2 Secondary endpoints and analysis method

[Secondary endpoints]

- Progression-free survival (PFS)

PFS is the period from the day of enrollment until the day of documented progression or the day of death due to all causes whichever comes earlier.

Progression will include both PD based on diagnostic imaging assessed according to RECIST ver 1.1 (see Appendix A) and primary disease progression that cannot be confirmed by diagnostic imaging (clinical progression). When progression is documented by diagnostic imaging, the day that the diagnostic imaging is performed will be the progression date. For clinical progression, the day of the clinical determination will be the progression date. In a case where, for example, tumor diameter has become extremely small, if the status is determined to be “not definite progression” clinically, although the assessment is PD according to the response criteria, the assessment of PD according to the response criteria will take precedence and the status will be considered progression. (In this case, the clinical determination on continuing protocol treatment will take precedence.) Even if the assessment is not PD according to the response criteria, if there is definite clinically documented progression, the clinical determination will take precedence and the status will be considered progression. For surviving subjects without documented progression, the period will be cut off on the final day when a progression-free status is confirmed (final day of confirming progression-free survival). Confirmation of progression-free status by imaging test or sample test is not mandatory, and clinical confirmation by outpatient medical examination, etc., will be allowed. Contact by

CONFIDENTIAL

telephone only will not be allowed.) Events and the cut-off will also be handled the same way in subjects who have discontinued protocol treatment for reasons such as toxicity and refusal of treatment, even if another (follow-up) therapy is added. Thus, the time of treatment discontinuation or the day of follow-up treatment initiation will not be the cut-off.

[Analysis method]

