7.2.4 Efficacy analysis

7.2.4.1 Primary endpoint and analysis method

[Primary endpoint]

Progression-free survival (PFS rate) at 6 months after enrollment

The PFS rate 6 months after enrollment, the primary endpoint, is the gross proportion of surviving subjects without documented progression up to 6 months after enrollment (date of enrollment + 24 weeks \pm 2 weeks), counting from the day of enrollment. Subjects with no imaging data on progression at 6 months after enrollment and subjects lost to follow-up will be included in the denominator, but will not be handled as progression-free.

Definition of progression:

Progression will include both progressive disease (PD) based on diagnostic imaging assessed according to RECIST ver. 1.1 and primary disease progression that cannot be confirmed by diagnostic imaging (clinical progression). When progression is documented by diagnostic imaging, the day on which the diagnostic imaging is performed will be the progression date. For clinical progression, the day of the clinical determination will be the progression date. In a case in which, for example, tumor diameter has become extremely small, if the status is determined to be “not definite progression” clinically, although the assessment is PD according to the response criteria, the assessment of PD according to the response criteria will take precedence and the status will be considered progression. (In this case, the clinical determination on continuing protocol treatment will take precedence.) Even if the assessment is not PD according to the response criteria, if there is

definite clinically documented progression, the clinical determination will take precedence and the status will be considered progression. For surviving subjects without documented progression, the period will be cut off on the final day when a progression-free status is confirmed (final day of progression-free survival confirmation). Confirmation of progression-free status by imaging test or sample test is not mandatory, and clinical confirmation by outpatient medical examination, etc., will be allowed. Contact by telephone only will not be allowed. Events and the cut-off will also be handled the same way in subjects who have discontinued protocol treatment for reasons such as toxicity and refusal of treatment, even if another (follow-up) therapy is added. Thus, the time of treatment discontinuation or the day of follow-up treatment initiation will not be the cut-off.

[Main analysis]

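### A new lesion that is doubtful on one scan and confirmed on a later one is dated to the later scan, which lengthens PFS and DOR and can, in a narrow case, add a success to the 6-month PFS rate

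*Protocol*

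**What the plan says.** Protocol Appendix A, section 7, deals with a possible new lesion that cannot yet be confirmed: "it should not be determined as a new lesion but re-examination by imaging test should be conducted after clinically appropriate interval". If the re-examination confirms it, "the date of the imaging test that confirmed the new lesion will be the time point for appearance of new lesion". No length is given for the interval.

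The progression definition in protocol 13.3.3.2 follows the same logic: "When progression is documented by diagnostic imaging, the day that the diagnostic imaging is performed will be the progression date". SAP 7.2.4.1 repeats it: "the day on which the diagnostic imaging is performed will be the progression date". The one override is clinical: "if there is definite clinically documented progression, the clinical determination will take precedence and the status will be considered progression".

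The primary endpoint (protocol 13.3.3.1) "is the gross proportion of surviving subjects without documented progression up to 6 months after enrollment", and the 6-month point "is defined as 24 weeks (8 weeks x 3) with time window of 2 weeks before and after". A subject without 6-month imaging, or lost to follow-up, stays in the denominator as a failure. Protocol 13.3.3.1 and SAP 7.2.4.1 also count an *unconfirmed* category at 6 months, but neither defines it.

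**The concern.** A confirming re-examination shows that the finding on the earlier scan was already tumour. Dating progression to the second scan credits the subject with progression-free time after the lesion was visible. Compared with dating to first sight, the rule can only delay progression, never advance it.

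The setting gives no internal correction. The trial is single-arm and open-label, the investigator reads the scans (protocol 9.2.10), and the result is tested against a fixed 29%. No concurrent arm shares the delay. The sensitivity analyses in SAP 7.4 vary only the handling of follow-up treatment, so the effect of the dating rule would not be seen in the planned output.

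**Working it through.** **1. Path of a doubtful lesion through the rules.** At the first scan the lesion is not called new, so the new-lesion column of Table A.1 reads absent and the overall response can be CR, PR or SD. The subject has imaging, so the missing-imaging failure rule does not apply. A doubtful lesion alone is not definite clinical progression. On confirmation, PD carries the date of the second scan. PFS and DOR gain the interval between the two scans.

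**2. Timing.** Inputs: scans every 56 days from Day 1 of Course 1 (protocol 9.2.10), ±7 days (Table 9.c); treatment starts within 14 days of entry in principle (8.1); the window closes at Week 26, day 182 from enrollment.

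- Day of the third scan from enrollment = start delay + 168 + slip. Range: 0 + 168 − 7 = 161 to 14 + 168 + 7 = 189, or Weeks 23 to 27.
- Days left in the window = 182 − scan day. On-time scan, no delay: 182 − 168 = 14. On-time scan, 14-day delay: 182 − 182 = 0. The most possible is 182 − 161 = 21.
- Next on-schedule scan: 168 + 56 = 224 to 182 + 56 = 238 days, or Weeks 32 to 34, outside the window.

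A re-examination that confirms the lesion by Week 26 still counts as progression at 6 months. One at the next scheduled scan does not. A lesion doubtful on an earlier scan and confirmed by Week 26 alters the PFS time but not the 6-month status.

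**3. The plan's own figure.** Exact binomial, 29% against 48%, one-sided 5%: at n = 47 the critical value is 20, the exact error 3.3% and the power 81.4%. At n = 46 the power is 77.6%. The stated 47 is reproduced, and 47 × 1.1 gives about 52.

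**4. Effect on the primary test.** Let m be the average number of affected subjects among 52 (an assumption). The chance of a positive result at a true rate of 29% is P(X ≥ r), with X binomial(52, 0.29 + m/52). Each affected subject adds 1/52 = 1.9 points to the rate. The documents give the one-sided level as 5% in some places (protocol 6.2.2.2 and 13.3.3.4, SAP 7.2.4.5) and 2.5% in others (protocol 13.3.3.1, SAP 7.2.4.1). That is a separate matter to reconcile, so both are shown.

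| m | success rate used | 5% test, r = 22 | 2.5% test, r = 23 |
|---|---|---|---|
| 0 | 29.0% | 2.8% | 1.4% |
| 0.5 | 30.0% | 3.9% | 2.1% |
| 1 | 30.9% | 5.5% | 3.0% |

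**5. How large could m be?** Assume exponential PFS with 29% progression-free at Week 24. Then 0.29^(16/24) = 43.8% are progression-free at Week 16, and (0.438 − 0.29) × 52 = 7.7 subjects progress between Weeks 16 and 24. One affected subject is 1/7.7 = 13% of these; two are 26% and three 39%.

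**The case against.** The strongest reply is that the case is narrow. A reader might infer that any lesion visible on the 24-week scan is scored progression-free. That is not so: a recognisable new lesion is PD at once, and only one that cannot be confirmed is deferred. Appendix A calls for a dedicated re-examination, not a wait for the next routine scan, so the 8-week delay is a possible route and not what the rule prescribes. This stands, and it limits the claim. The interval is nevertheless left open, and the window leaves 14 days or fewer for an on-time scan.

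Nor is the affected subject certain to count as a success. The *unconfirmed* category could be read to include a lesion awaiting re-examination, and protocol 13.3.1 and SAP 7.1 allow handling rules to be added before data fixation. But no such rule is written.

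A reader might also carry the calculation on to an average of two or three subjects, where the 5% test would reach 9.8% or 16.0%. The documents give no frequency, and step 5 shows these values would need a quarter to two-fifths of all progressions in that interval to be of this one kind. They should not carry the argument.

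Finally, bias against the 29% threshold is not shown. The documents do not say how the ASPECCT study, from which 29% is taken, dated such lesions. If it used the same rule, the delay is already in the threshold.

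**Conclusion.** The point holds in limited form. The dating rule is explicit, no other provision reverses it, and its direction is fixed: PFS and DOR can only be lengthened. For the 6-month rate it matters only when the lesion is first doubtful on the scan nearest Week 24, no other PD, death or definite clinical progression occurs, and confirmation falls after Week 26, and then only if the subject is not placed in the *unconfirmed* category.

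The size rests on an assumed frequency. At an average of half a subject in 52 the error stays below nominal at either level; at one subject it passes slightly above. This does not show that the trial's conclusion would be wrong. It is a small, avoidable, one-directional effect in an uncontrolled test, and worth removing because the correction is cheap.

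**What to change.** - **Dating.** In Appendix A, section 7, and in the progression definition in protocol 13.3.3.2 and SAP 7.2.4.1, state: if re-examination confirms a new lesion, the progression date for the PFS rate, PFS and DOR is the date of the scan on which the lesion was first seen; if it is not confirmed, the earlier assessment stands.
- **TTF.** Leave it on the day of the PD decision, as SAP 7.2.4.2 has it. Back-dating it would end TTF while the subject was still on protocol treatment.
- **Lesions never resolved.** Define *unconfirmed* so that a lesion still doubtful at 6 months and never re-imaged falls in it and is not counted as progression-free.
- **Sensitivity analysis.** Report the result under the present dating rule beside the analyses in SAP 7.4.

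The cost is these text changes, a CRF flag or query for the date a later-confirmed lesion was first seen, and a PFS rate that may be slightly lower. No extra scans are needed, and treatment decisions still follow the re-examination.
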